The overall aim of the study is to evaluate the impact of a mental health care system on improving population level mental health of children in refugee settlements, with the following guiding research questions and hypotheses:

Research questions (RQ) and hypothesis

[RQ1] What is the population-level effectiveness of a multi-level multi-component care system on improving the wellbeing amongst adolescents (aged 11-16), and/or reducing depression, anxiety and externalizing symptoms amongst adolescents (aged 11-16 years) with elevated levels of emotional distress?

¹ A separate protocol will be developed and submitted describing a study that will be embedded within the main trial to evaluate how a care system performs in a real-world context (e.g. care pathways, quality of care, coverage etc.)

Hypothesis: Children in the experimental arm (i.e. mental health care system) regardless of whether and what services they received will have a greater improvement in wellbeing and/or reduction in depression, anxiety and internalizing symptoms amongst those with elevated levels at baseline, over a period of 12 months compared with children in the control arm (i.e. waitlist control).

[*RQ2*] What are the synergistic and indirect effects of a multi-level and multi-component care system and the associated cost-benefits?

Objectives: (i) Improve understanding of whether and what combination of interventions result in better mental health outcomes (i.e. relative contribution to outcomes by different component parts) – amongst the group of children receiving services; (ii) Improve understanding of the indirect effects of a mental health care system approach on other life domains, i.e. to what extent does the mental health care system result in effects beyond the intended (mental health) outcomes (i.e. school outcomes, bullying victimization or perpetration, domestic (parental) or intimate partner violence victimization or perpetration, risky sexual behavior, illegal substance use, child labor, early marriage). (iii) Improve understanding of the population-level cost-effectiveness of the mental health care system.

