2. METHODS

[figure not shown]
2.1.Design

The primary study design [RQ1] will be a pragmatic parallel two-arm cluster Randomized Controlled Trial (cRCT), randomizing 18 zones (i.e. clusters; a zone is an administrative unit in Uganda) in a 1:1 ratio (stratified for school size) to one of the two study arms (see Figure 1). The two arms are the multi-component mental health care system (experimental arm) vs waitlist control. A random population sample of children (age 11-16) will be drawn from schools (one school per cluster) from the selected zones and follow-up 6 and 12 months later, wherein the type and extent of services received by children in the experimental arm is not a priori defined following a naturalistic service delivery framework (i.e. not all children and their caregivers will participate in the interventions, further explained below). This means that some children and their caregivers that are part of the experimental arm will not receive any service, and other children and their caregivers receive all available services that are part of the care system (see further details under 'Sample' below). Furthermore, children and their caregivers that are not part of the

study sample but are part of the enrolled schools in the experimental arm may also receive any or all the services being offered in the care system. This means that children that have been recruited into the study may benefit from the mental health care system either directly (i.e. receiving services) and/or indirectly (i.e. through peers and caregivers receiving services).

The rationale for this approach is to be able to assess the *population-level*² effect of a mental health care system, rather than a *participant-level effect*. Given the pragmatic implementation, intention-to-treat will be our primary analysis framework. A cRCT was selected because of the potential contamination of the implementation of a multi-component mental health care system that involves children, their caregivers and school-personnel. (*See Figure 1 for study flowchart*).

Figure 1. Flowchart

Note: All T0 and T2 assessments include children and their caregivers, T1 consists of a shortened version of the adolescent surveys only.

[figure not shown]

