Embedded sub-studies to evaluate synergistic effects, indirect effects, and cost-effectiveness [RQ2]. First, through a surveillance design we will track which children, and their caregivers get which services at what point in time throughout the implementation period (1 school year). This allows for analyses of a sub-sample of the cRCT that receives any of the interventions to investigate whether different combinations of interventions result in different outcomes. Second,

² Population level in this protocol refers to 'population of school-going children'.

the cRCT study will allow for secondary analyses to investigate the degree by which participants in the experimental arm show benefits in other outcomes related to schooling and child labor, violence, substance use, risky (sexual) behavior and early marriage. Third, we will also conduct an economic evaluation, in which we will examine costs and possible offsets of delivering the care system implementation and assess the cost-effectiveness of the program. The purpose will be to gather relevant information about the potential economic value of the interventions.

2.2.Setting

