2.3.1. Mental health care system

War Child has implemented a suite of core interventions working across multiple ecological levels and that target multiple dimensions of mental health and psychosocial wellbeing among children, adolescents, parents/caregivers, teachers, and their communities. These interventions have been implemented and tested according to a systematic approach for developing and evaluating services for children and adolescents affected by armed conflict (War Child, 2022). This multiphase process includes steps to adapt interventions to local community contexts, as well as to consult or partner with community stakeholders as appropriate. Through this process, and through work in multiple conflict-affected country contexts, War Child has gathered a strong evidence base demonstrating the feasibility, acceptability, and effectiveness of these individual interventions. This set of tested interventions are conceptually interconnected in terms of their theories of change, design, objectives, and potentials for cross-referrals. We propose to now link these interventions in practice; (a) by packaging them together as a novel, multidimensional, ecologically nested, community-based mental health care system model; and (b) by testing the synergistic impacts of this model on child and adolescent psychosocial wellbeing.

Below is a brief presentation of the interventions that make up the mental health care system that is being developed. See also Figure 2. All interventions (except Community Tales) have gone through rigorous effectiveness research as a stand-alone intervention. All interventions will go

through, or already have gone through, a systematic process of adaptation to the cultural context of this study, specifically for refugee populations primarily from the DRC in western Uganda – this process includes (i) translation of materials, (ii) cognitive interviewing to ensure understanding of the materials, (iii) pilot-testing of the adapted materials.

Figure 2. Care System

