Implementation model for the care system follows a pragmatic approach. This means that implementation is offered and implemented as it would be in a real-world context, rather than highly controlled (as would be the case in regular efficacy trials). Pragmatic implementation means that we accept close to real-world conditions and that we do not work with pre-set targets for participants (see also under sample below). In the case of the above-mentioned interventions, this means: First, within all enrolled schools all school personnel will be invited to participate in Community Tales workshops. Second, using schools as the entry point, TeamUp will be offered to P1-P6 school classes including children aged 11-16 over the period of 12 months. Importantly, planning of TeamUp will have two restrictions; (1) implementation will follow a randomized rotation system of classes to avoid bias of sequence, and (2) 10-20% randomly selected classes will be excluded from receiving TeamUp (because in real-world implementation contexts not all children can be reached by mental health interventions, yet we still want to evaluate the population-level effects, our design deliberately excludes classes from participation). TeamUp will be implemented as an extra-curricular activity, and participation for children is voluntary. Third, the caregiver support intervention, BeThere, is open to any caregiver with children between 3-16 years of age in the catchment area of the enrolled schools. Caregivers are recruited via information sessions that are held at school and the community-at-large about the availability and aims of BeThere. Fourth, ReachNow is implemented by TeamUp facilitators, as well as other selected community gatekeepers (i.e. trusted and respected members in the community). Selection of community gatekeepers (other than TeamUp facilitators) will be determined for each catchment area for each enrolled school, aiming for a rate of 1 trained gatekeeper per 3000 zone population. The number of gatekeepers per zone is dependent on the population size in the zone, our aim is to train 1 gatekeeper per 3000 residents. They include: Village Health Teams (VHTs), teachers, group activity facilitators, child protection committee members, local community leaders and refugee committee leaders. Specific inclusion criteria are: 18 years of age; trusted and respected members from the community; engaged in promoting child wellbeing; access to children, adolescents and caregivers; demonstrate high level of empathy and interest in children's wellbeing; willing to provide informed consent and participate in supervision meetings to provide feedback on feasibility of the approach; willing to sign and follow WCH's Child Safeguarding Policy, Code of Conduct and Code of Ethical conduct in using the CCDT. Upon detection of children in need of mental health care (of children in and out of schools), using the ReachNow tool, these children will be referred to Project Officers Psychosocial support (PO PSS)/case worker who will then refer to EASE facilitators (for children 11-16 years) and to external referral

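### RQ2 asks about synergy, but objective (i) analyses only children who received services and names only a comparison between combinations, which leaves out the no-service reference and cannot separate synergy from additive benefit

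*Protocol*

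**What the plan says.** Section 1.3 of the Protocol poses RQ2 as "What are the synergistic and indirect effects of a multi-level and multi-component care system and the associated cost-benefits". Section 2.3.1 gives, as one of two steps in linking the interventions, "by testing the synergistic impacts of this model on child and adolescent psychosocial wellbeing". Section 2.1 names synergistic effects among the targets of the embedded sub-studies.

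The analysis set is narrower than the question. Objective (i) in Section 1.3 speaks of what each component adds ("i.e. relative contribution to outcomes by different component parts) – amongst the group of children receiving services"). Section 2.1 says that service tracking allows "analyses of a sub-sample of the cRCT that receives any of the interventions", in order to "investigate whether different combinations of interventions result in different outcomes". No interaction or departure from additivity is mentioned. Item (ix) of Section 2.10.1 lists the analysis of relative contributions and names no analysis set.

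A no-service group exists. Section 2.1 says that "some children and their caregivers that are part of the experimental arm will not receive any service", and these children are followed up like the others. Sections 2.1 and 2.8.4 add that trial children may also benefit indirectly, for example through peers who receive services.

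Section 2.3.1 states that "within all enrolled schools all school personnel will be invited to participate in Community Tales workshops", and it plans ReachNow gatekeepers for the catchment area of every enrolled school.

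**The concern.** Synergy between components A and B normally means that the pair does more than the sum of its parts: Y(A+B) − Y(A) − Y(B) + Y(none). Restricting the analysis to children with at least one service removes Y(none). The contrast that remains, a combination against a single component, is expected to be positive whenever the added component works, even with no synergy at all. This is a matter of the analysis set and the contrast. It would apply even if receipt of services had been randomised.

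At stake is a named research question, and one of the two stated steps in joining the interventions into a system. As the objective is set, the sub-study could yield a result that reads as support for synergy when it shows only that two helpful things help more than one.

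**Working it through.** **Plan figures.** The Protocol gives no sample size or precision for RQ2. Section 2.8.3 gives 18 clusters (9 per arm), 176 analysed children per cluster and 30% loss: 176 / 0.70 = 251.4, so 252 per school, and 252 × 18 = 4,536, which reproduces the plan. The experimental arm at endline is then 9 × 176 = 1,584 children.

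**Step 1: which terms can be estimated.** Code receipt of each component as 0 or 1 and compare the rank of the design with the number of parameters.

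| Model | Parameters | Rank, all | Rank, recipients only |
|---|---|---|---|
| Two components, with interaction | 4 | 4 | 3 |
| TeamUp, EASE, BeThere, pairwise terms | 7 | 7 | 7 |
| The same, with three-way term | 8 | 8 | 7 |

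With two components the interaction is lost. With three, pairwise terms remain if no three-way interaction is assumed or, equivalently, as interactions within recipients of the third component. The three-way term is lost, and so is any pairwise synergy measured against no service.

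**Step 2: what the stated contrast can show.** Take assumed recipient means A = 0.15, B = 0.15 and A+B = 0.30 SD. The recipients-only contrast is 0.30 − 0.15 = 0.15 SD whatever the no-service mean is. The interaction is 0.30 − 0.15 − 0.15 + Y(none):

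- Y(none) = 0: interaction 0.00 (purely additive)
- Y(none) = 0.15: interaction +0.15 (synergy)
- Y(none) = −0.15: interaction −0.15 (antagonism)

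The recipient data are identical in all three cases.

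**Step 3: precision.** The documents give no reach, so assume TeamUp 60%, EASE 15%, BeThere 15%, independent receipt, outcome SD 1 and no clustering. Expected cell sizes out of 1,584:

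- no service 458; TeamUp only 687; EASE only 81; BeThere only 81
- TeamUp+EASE 121; TeamUp+BeThere 121; EASE+BeThere 14; all three 21

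Among recipients, seven cells carry seven parameters, so each pairwise SE is the root of the summed reciprocals of the four cells that share the third component.

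- TeamUp × EASE, within BeThere: √(1/81 + 1/14 + 1/121 + 1/21) ≈ 0.37 SD
- EASE × BeThere, within TeamUp: √(1/687 + 1/121 + 1/121 + 1/21) ≈ 0.25 SD

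With the no-service children kept, weighted least squares for the pairwise model gives 0.14 SD for TeamUp × EASE and 0.20 SD for EASE × BeThere. By symmetry, TeamUp × BeThere equals TeamUp × EASE.

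Over an assumed reach of 50–75% for TeamUp and 10–20% for each of the others, the TeamUp × EASE SE runs from 0.28 to 0.61 SD among recipients and from 0.13 to 0.19 SD with everyone. The group left out would number about 250 to 640 children.

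**Step 4: direction.** With assumed additive effects of 0.20, 0.15 and 0.10 SD (TeamUp, EASE, BeThere) and no synergy, children with two or more components average 0.145 SD better than those with one (SE 0.069), and about 55% of such trials would be significant. If EASE recipients carry an assumed residual need deficit of 0.3 SD, the contrast falls to about 0.00 SD, with about 3% significant in favour of the combination.

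**The case against.** The other side has five points.

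- *Synergy is not wholly out of reach.* A reader might infer that recipients-only data can say nothing about synergy. That is too strong: three components are tracked, all four EASE × BeThere cells exist among TeamUp recipients, and the precision loss for that pair is modest. This stands. What is lost is synergy against no service and the three-way term, with a heavy loss for pairs that involve TeamUp.
- *The Protocol does not say it will call a better combination synergy.* A reader might also infer that an additive package would be reported as a superior or synergistic combination. The documents settle neither. EASE follows referral (Section 2.3.1) and TeamUp is voluntary, so combinations could look better, null or worse. If a combination did better because effects add up, saying so would be a correct answer to objective (i). Only the step to synergy would be wrong.
- *The model belongs in the statistical analysis plan.* This is true of model terms. But the Protocol itself fixes the analysis set in the research objective and again in the design section. Item (ix) of Section 2.10.1 does not lift it, so a plan that follows the Protocol inherits the gap. The wording in Section 2.1 ("This allows for analyses of a sub-sample of the cRCT that receives any of the interventions to investigate") is permissive, which softens the point without removing it.
- *No-service children are not a clean reference.* They may benefit through peers, and they are unreferred or chose not to attend. This stands, and calls for adjustment and a caveat.
- *The repaired analysis is still weak.* At 80% power the detectable interaction is about (1.96 + 0.84) × 0.144 = 0.40 SD for TeamUp × EASE and 2.80 × 0.197 = 0.55 SD for EASE × BeThere, before clustering. Both exceed the d = 0.30 that the trial is sized for. This also stands.

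**Conclusion.** The point holds in a limited form. Question, analysis set and contrast do not match: RQ2 asks about synergy, objective (i) keeps recipients only, and the named comparison would be met by simple additivity. The gap in estimability follows from the cell structure and needs no assumption. The size of the precision loss (0.37 against 0.14 SD for pairs with TeamUp, 0.25 against 0.20 SD for EASE × BeThere) rests on assumed reach, independent receipt and no clustering.

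Separately, Community Tales and ReachNow are planned for every experimental school or its catchment. Their individual contributions cannot be isolated within the arm, although objective (i) promises contributions by component. Keeping the no-service children does not change that.

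RQ1 is untouched and RQ2 (i) is framed as improving understanding. This should be corrected, but it does not threaten the primary result.

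**What to change.** 1. In Section 1.3, objective (i), and in Section 2.1, extend the analysis set to all experimental-arm trial children, classified by child and caregiver receipt. Use those who, with their caregivers, received no service as the reference. State the same set in Section 2.10.1 (ix), which now names none.
2. Define synergy as departure from additivity on the score scale: product terms for TeamUp, EASE and BeThere with 95% confidence intervals, adjusted for baseline symptom level. Report combination-versus-single differences as added benefit.
3. State that the analysis is observational and exploratory, that no-service children may benefit indirectly through peers, and that the separate contributions of Community Tales and ReachNow cannot be isolated within the arm.
4. If this is not wanted, replace the term synergistic with comparative outcomes of combinations among service users.

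The cost is wording in three places and a few model terms. The children are already to be enrolled, measured and tracked, so no new data are needed. The price is a more modest claim: over the assumed reach, interval half-widths run from about 1.96 × 0.126 = 0.25 SD (pairs with TeamUp, best case) to 1.96 × 0.279 = 0.55 SD (EASE × BeThere, worst case), before clustering.

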2. METHODS

[figure not shown]
2.1.Design

The primary study design [RQ1] will be a pragmatic parallel two-arm cluster Randomized Controlled Trial (cRCT), randomizing 18 zones (i.e. clusters; a zone is an administrative unit in Uganda) in a 1:1 ratio (stratified for school size) to one of the two study arms (see Figure 1). The two arms are the multi-component mental health care system (experimental arm) vs waitlist control. A random population sample of children (age 11-16) will be drawn from schools (one school per cluster) from the selected zones and follow-up 6 and 12 months later, wherein the type and extent of services received by children in the experimental arm is not a priori defined following a naturalistic service delivery framework (i.e. not all children and their caregivers will participate in the interventions, further explained below). This means that some children and their caregivers that are part of the experimental arm will not receive any service, and other children and their caregivers receive all available services that are part of the care system (see further details under 'Sample' below). Furthermore, children and their caregivers that are not part of the

study sample but are part of the enrolled schools in the experimental arm may also receive any or all the services being offered in the care system. This means that children that have been recruited into the study may benefit from the mental health care system either directly (i.e. receiving services) and/or indirectly (i.e. through peers and caregivers receiving services).

The rationale for this approach is to be able to assess the *population-level*² effect of a mental health care system, rather than a *participant-level effect*. Given the pragmatic implementation, intention-to-treat will be our primary analysis framework. A cRCT was selected because of the potential contamination of the implementation of a multi-component mental health care system that involves children, their caregivers and school-personnel. (*See Figure 1 for study flowchart*).

Figure 1. Flowchart

Note: All T0 and T2 assessments include children and their caregivers, T1 consists of a shortened version of the adolescent surveys only.

[figure not shown]
Embedded sub-studies to evaluate synergistic effects, indirect effects, and cost-effectiveness [RQ2]. First, through a surveillance design we will track which children, and their caregivers get which services at what point in time throughout the implementation period (1 school year). This allows for analyses of a sub-sample of the cRCT that receives any of the interventions to investigate whether different combinations of interventions result in different outcomes. Second,

² Population level in this protocol refers to 'population of school-going children'.

the cRCT study will allow for secondary analyses to investigate the degree by which participants in the experimental arm show benefits in other outcomes related to schooling and child labor, violence, substance use, risky (sexual) behavior and early marriage. Third, we will also conduct an economic evaluation, in which we will examine costs and possible offsets of delivering the care system implementation and assess the cost-effectiveness of the program. The purpose will be to gather relevant information about the potential economic value of the interventions.

2.2.Setting

This study will be conducted with refugee populations in western Uganda, specifically the refugee settlements (Kyangwali, Kyaka and Nakivale) hosting displaced persons primarily from the DRC. Kyangwali hosts approximately 132000 refugees, 96% of whom are from DRC and 29% are below the age of 18. Kyaka hosts approximately 123000 refugees, 97% of whom are from DRC and 29% are below the age of 18. Nakivale hosts approximately 180000 refugees, 67% of whom are from DRC and 27% are below the age of 18. In all three locations most adults are crop farmers or farm laborers. These profiles are all based on OPM/UNHCR data. Uganda was selected as the site for this study because of its large refugee population, our extensive preliminary research in this setting, and because it exemplifies a low-resource setting where a mental health care system such as the one being evaluated in this study is relevant. Uganda is one of the largest refugeehosting nations in the world. Currently, Uganda hosts approximately 1.4 million refugees, primarily from South Sudan and the Democratic Republic of Congo – with more than 60% being children (UNHCR, 2019a; UNHCR, 2019b). The Ugandan's government has been quite welcoming towards refugees, providing them with a plot of land to encourage "self-reliance", as well as collaborating with humanitarian organizations to offer a variety of services. Still, the refugee influx increases pressure on already reduced resources, contributing to tensions between host and refugee communities (Adaku at al., 2016; Baron, 2002). Even when basic services (shelter, food, education) are available, children's psychosocial well-being is often overlooked, potentially leading to unidentified and unaddressed needs (Tol et al., 2015; Purgato et al., 2018).

Source: Refugees and Asylum-Seekers in Uganda as per September 2023 (UNHCR)

2.3.Intervention

[figure not shown]
